#### 6.11.2 Analysis of Secondary Endpoints

All secondary endpoints will be analyzed according to the procedure for continuous variables. Correlations (original data and changes from baseline) might be calculated.

#### 6.12 Analysis of Safety Data

The summary of safety will be performed based on the SAF.

#### 6.12.1 Vital Signs

Summaries of vital sign variables will include original data and change from baseline by visit.

Blood pressure will be analyzed only by PWA because these measurements are regarded as more precise.

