#### 4.8.2 Dropout patients

A subject who discontinues study participation prematurely for any reason is defined as a "dropout" if the subject has already been administered at least one dose of the study medication. Any subject removed (dropout) from the study will remain under medical supervision until discharge is medically acceptable. In all cases, the reason for withdrawal must be recorded in the

eCRF and in the subject's medical records. The sponsor has to be informed about dropout patients by the investigator.

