#### 4.13.3 Visit 2 and Visit 4 - Treatment phase

The following actions/measures will be performed for patients of Arm A and Arm B:

- assessment of adverse events
- questioning for concomitant medication
- clinical examination for potential bleeding sides
- measurement of blood pressure and heart rate (after resting for at least 3 min in supine position)
- return of study medication and drug accountability
- dispense of new study medication
- safety laboratory parameter

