#### 2.4 Sample size calculation

The first primary variable is the change of forearm blood flow with venous occlusion plethysmography ( $\Delta$ FBF) after forearm ischemia after 20 weeks of treatment. The sample size calculation is based on the following assumptions:

- Hypotheses: H0:  $\mu_{\Delta FBF, Riva} \leq \mu_{\Delta FBF, ASS}$ H1:  $\mu_{\Delta FBF, Riva} > \mu_{\Delta FBF, ASS}$
- Application of t-test for independent samples
- Type I error:  $\alpha = 0.05$
- Power: 1-ß = 0.90
- Estimated dropout rate: 25 %
- Minimum of expected clinical relevant difference between the groups in changes of maximal forearm blood flow ( $\Delta$ FBF) = 1.2 ml/100ml with an estimated standard deviation (STD)  $\sigma$  = 2.4 ml/100ml

Sample size should be at least N = 188 Patients (i.e. N/2 = 94 patients per arm) in order to achieve a valid number of 141 patients (per protocol analysis).

Additionally, the second primary variable is the difference of PWV between treatment groups at EOT Extension (after 52 week of treatment). The sample size calculation is based on the following assumptions:

H0: μPWV, Riva = μPWV, ASS

• H1:  $\mu_{PWV, Riva} \neq \mu_{PWV, ASS}$ 

• Type I error:  $\alpha = 0.05$ , t-test for independent samples

• Power: 1-ß = 0.80

Estimated dropout rate: 20 %

• Minimum of expected clinical relevant difference between the groups in PWV = 0.7 m/s with an estimated standard deviation (STD) of  $\sigma$  = 1.0 m/s

Sample size should be N=80 patients (40 patients per arm) to achieve a valid number of 66 patients for per protocol analysis.

In summary the necessary sample size would be N=188 patients for the study up to week 20 including 80 patients for the extension up to week 52.

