#### 4.5 Efficacy Variables

Efficacy variables will be measured at day 0, weeks 20 and week 52:

Forearm blood flow (FBF) (mL/100mL): IR baseline, IR post-ischemic, IR post-ischemic (AUC)

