#### Extension:

Arterial stiffness measured by pulse wave analysis: Pulse wave velocity (m/s), index of augmentation (%), peripheric and central blood pressure systolic/diastolic (mmHg)

Skin blood flow (measured by Laser Doppler):

Depth pre-ischemic blood flow (U), depth post-ischemic blood flow (U), shallow pre-ischemic blood flow (U) and shallow post-ischemic blood flow (U)

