#### 4.7 Safety Variables

#### 4.7.1 Vital Signs

Vital Signs will be collected in terms of:

Height (cm) (day 0, week 52)

Weight (kg), BMI (kg/m2), Waist and Hip circumference (cm) (day 0, weeks 2, 8, 20, 28, 36, 52) Radial pulse (bpm), systolic/diastolic blood pressure (mmHg) (day 0, weeks 2, 8, 20, 28, 36, 52)

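### Restricting blood pressure analysis to PWA leaves clinic readings at weeks 2, 8, 28 and 36, and all on-treatment pressures of patients who leave before week 20, out of every by-arm summary

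*SAP*

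**What the plan says.** SAP 4.7.1, under the safety variables, sets the clinic schedule: "Radial pulse (bpm), systolic/diastolic blood pressure (mmHg) (day 0, weeks 2, 8, 20, 28, 36, 52". The protocol visit lists agree. Section 4.13.3 (weeks 2 and 8) includes "measurement of blood pressure and heart rate (after resting for at least 3 min in supine position", section 4.14.2 (weeks 28 and 36) has the same item, and neither list contains an arterial stiffness measurement.

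SAP 6.12.1 opens with a general rule: "Summaries of vital sign variables will include original data and change from baseline by visit". It then makes an exception for one variable: "Blood pressure will be analyzed only by PWA because these measurements are regarded as more precise".

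The PWA variables appear in SAP 4.5 as "Pulse wave velocity (m/s), index of augmentation (%), peripheric and central blood pressure systolic/diastolic (mmHg", and the timing given there is: "Efficacy variables will be measured at day 0, weeks 20 and week 52". SAP Tables 1 and 2 mark arterial stiffness at V1, V6 and V13 only, and the PWA mock tables in SAP 7.6.2 show the same three time points.

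The vital-signs mock tables in SAP 7.8.1 name height, weight and radial pulse, followed by an open row for other variables. Blood pressure is not named. Radial pulse is shown at all seven visits, as is haemoglobin in the safety laboratory mock table (SAP 7.8.2).

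**The concern.** The stated reason is precision. That can justify choosing PWA over the cuff where a patient has both readings at the same visit. It does not justify leaving out cuff readings at visits where no PWA reading exists, because nothing replaces them. Pulse shares a line and a schedule with blood pressure in SAP 4.7.1 and keeps its by-visit summary. Only blood pressure loses it.

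The protocol treats blood pressure as relevant to safety. Sustained uncontrolled hypertension is an exclusion criterion that applies before and during the trial (4.11.2). Uncontrolled severe hypertension is listed among conditions with increased bleeding risk, and hypotension among the common reactions to rivaroxaban (Table 11). The readings at weeks 2 and 8 are the only scheduled on-treatment pressures before week 20. Without them, a shift between arms early in treatment, or one confined to patients who stop early, would not show in any summary table.

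**Working it through.** **1. Visits affected.**
- Clinic pressure on treatment (SAP 4.7.1): weeks 2, 8, 20, 28, 36, 52.
- PWA pressure on treatment (SAP 4.5, Tables 1 and 2): weeks 20, 52.
- Clinic without PWA: weeks 2, 8, 28, 36.

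That is 4 of 6 time points overall, made up of 2 of 3 in the main period (all patients) and 2 of 3 in the extension (80 patients).

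**2. Scheduled readings, assuming full attendance.** Inputs: 188 patients to week 20, of whom 80 continue to week 52 (SAP 2.4).
- Clinic: 188 × 3 + 80 × 3 = 564 + 240 = 804.
- PWA: 188 × 1 + 80 × 1 = 268.
- Not summarised: 804 − 268 = 536, and 536 / 804 = 67%. Of these, 188 × 2 = 376 fall in the main period and 80 × 2 = 160 in the extension.

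**3. The plan's own figure.** SAP 2.4 gives "Estimated dropout rate: 25"%, with 188 patients planned for 141 valid. For a difference of 1.2, an SD of 2.4, one-sided α = 0.05 and 90% power, the exact t-test needs 70 per arm, or 140 in total. Then 140 / 0.75 = 187 after rounding up, against the plan's 188, and 188 × 0.75 = 141. The plan's figures are reproduced.

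**4. Patients with no on-treatment pressure in a summary.** Upper bound = 188 × proportion leaving before week 20.

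| Proportion leaving before week 20 | Patients |
|---|---|
| 10% (assumed) | 18.8, about 19 |
| 25% (the whole planned loss) | 47 |
| 35% (assumed) | 65.8, about 66 |

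A treated patient who leaves before V6 is in the safety set (SAP 3.2). For such patients, protocol 4.8.2 provides this: "Any subject removed (dropout) from the study will remain under medical supervision until discharge is medically acceptable". It also requires the reason to be recorded, but it describes no early-termination visit with PWA. SAP 6.3 rules out imputation. Patients who leave after week 20 keep their week-20 PWA value and are not counted here.

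**The case against.** The strongest reply is that this is a pre-specified choice of method, with a stated reason, for a variable that is not an endpoint. Much of that stands, and several stronger readings that might be drawn from the passage are not supported.

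- *That clinic pressures are discarded or never reported.* Protocol 9.2 provides in general for listings of all data per subject and visit, and SAP 6.10 summarises baseline vital signs by arm. What is lost is the on-treatment summary and comparison by arm. Listings do not readily show a shift between groups. The SAP names no vital-signs listing, and the open row in SAP 7.8.1 cannot outweigh an explicit restriction in the text.
- *That SAP 6.12.1 contradicts itself.* It reads more naturally as a general rule followed by a named exception.
- *That the interpretation of PWV suffers.* PWA pressure is available at every visit where PWV is measured, so this does not follow.
- *That unsafe individual pressures would be missed.* Abnormal signs can be recorded as adverse events, adverse events are asked about at each visit, and protocol 4.8.1 covers patients who develop an excluding condition. Individual detection does not depend on a summary table. Nor do the documents say that safety problems concentrate among early leavers.
- *That 47 patients will have no pressure analysed.* The 25% loss leads to a per-protocol number. A patient excluded for a major deviation who still attends V6 does contribute PWA pressure. A patient who leaves before week 2 has no scheduled on-treatment clinic reading either, so the fix would not recover everyone. The documents are silent on whether early leavers receive an end-of-treatment assessment.

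**Conclusion.** The point holds as a minor reporting gap in the safety analysis. Under SAP 6.12.1, clinic pressure at weeks 2 and 8 (all patients) and weeks 28 and 36 (extension patients) enters no by-arm summary, and treated patients who leave before week 20 are absent from every on-treatment blood pressure summary. The list of visits follows directly from the two schedules. The 67% assumes full attendance. The 47 of 188 is a ceiling that assumes the whole 25% loss is departure before week 20 with no PWA at exit. Neither primary endpoint, the bleeding analysis nor the sample size is touched.

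**What to change.** In SAP 6.12.1, limit the sentence so that PWA is the preferred method for inference where both measurements exist. Add a descriptive summary in the safety set, without significance tests, of clinic systolic and diastolic pressure and change from baseline, by visit and arm. Include the last on-treatment value for patients who leave early. Name the two variables in the SAP 7.8.1 mock tables, but do not copy the pulse layout unchanged, because it carries p-values at each visit and would add repeated tests on a second method.

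The cost is one descriptive table. A second blood pressure method will also stand beside PWA at weeks 20 and 52, so a line is needed to say which one carries the inference. No new visit, measurement, alpha or sample size is required.

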#### **6.12.2 Safety Laboratory Measurements**

Summaries of safety laboratory variables will include:

- Descriptive statistics of original values and differences from baseline
- The number (n) and percentage (%) of subjects with CSVs during study, depending on data.

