#### 4.11.2 Exclusion criteria

Subjects are to be excluded from the study if they display any of the following criteria before and during the trail:

- major CV event with need for oral anticoagulation or platelet inhibitor therapy or acute coronary syndrome < 12 month before study entry

- sustained uncontrolled hypertension: systolic blood pressure > 180 mmHg or diastolic blood pressure > 100 mmHg
- hypersensitivity to the active substance or to any of the excipients
- active clinically significant bleeding
- lesion or condition, if considered to be a significant risk for major bleeding, this may include
  - active internal bleeding
  - platelet count < 100.000/µL at the screening visit
  - current or recent gastrointestinal ulceration,
  - presence of malignant neoplasm at high risk of bleeding,
  - recent brain or spinal injury, recent brain, spinal or ophthalmic surgery,
  - recent intracranial haemorrhage,
  - known or suspected oesophageal varices, arteriovenous malformations, vascular aneurysms or major intraspinal or intracerebral vascular abnormalities.
- concomitant treatment with any other anticoagulants e.g. unfractionated heparin (UFH), low
- molecular weight heparins (enoxaparin, dalteparin, etc.), heparin derivatives (fondaparinux, etc.), oral anticoagulants (warfarin, dabigatran etexilate, apixaban, etc.) except under the circumstances of switching therapy to or from rivaroxaban or when UFH is given at doses necessary to maintain an open central venous or arterial catheter
- concomitant treatment of ACS with antiplatelet therapy in patients with a prior stroke or a transient ischaemic attack (TIA)
- hepatic disease associated with coagulopathy and clinically relevant bleeding risk including cirrhotic patients with Child Pugh B and C
- chronic renal failure with eGFR < 15 ml/min (MDRD formula)

- as with other antithrombotics, rivaroxaban is not recommended in patients with an increased bleeding risk such as:
  - congenital or acquired bleeding disorders
  - uncontrolled severe arterial hypertension
  - active ulcerative gastrointestinal disease

- vascular retinopathy
- bronchiectasis or history of pulmonary bleeding
- known HIV infection at time of screening
- known hypersensitivity to the active substance or to any of the excipients
- Pregnant or breast-feeding woman and woman without adequate method of contraception.

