## 10 Safety

## 10.1 Definitions of adverse events and adverse drug reactions

### 10.1.1 Adverse event

An adverse event (AE) is any untoward medical occurrence (i.e. any unfavorable and unintended sign [including abnormal laboratory findings], symptom or disease) in a patient or clinical investigation subject after randomization /first intake of study medication in the study. Therefore, an AE may or may not be temporally or causally associated with the use of a medicinal (investigational) product.

A surgical procedure that was planned prior to the start of the study by any physician treating the subject should not be recorded as AE (however, the condition for which the surgery is required may be an AE).

In the following differentiation between medical history and AEs, the term "condition" may include abnormal e.g. physical examination findings, symptoms, diseases, or laboratory or ECG test results.

- Conditions that started before signing of informed consent and for which no symptoms or treatment are present until signing of informed consent are recorded as medical history (e.g. seasonal allergy without acute complaints).
- Conditions that started before signing of informed consent and for which symptoms or treatment are present after signing of informed consent, at unchanged intensity, are recorded as medical history (e.g. allergic pollinosis).
- Conditions that started or deteriorated after signing of informed consent will be documented as adverse events.

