#### 4.7.2 Safety laboratory

Safety laboratory variables will be monitored (day 0, weeks 2, 8, 20, 28, 36, 52): hemoglobin, hematocrit, ALAT, ASAT, creatinine (PAP method), blood cell count (leucocytes, erythrocytes, platelets), total bilirubin, sodium, potassium, eGFR

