#### 6.2 Descriptive or summary statistics

All continuous variables will be summarized by treatment group using the following statistics: n (non-missing sample size), number of missing values (Missing), arithmetic mean (Mean), standard deviation, (STD), median (Median), maximum (Max) and minimum (Min).

Tables for original (untransformed) data will be provided as well as tables for differences from baseline by visit. Boxplots will be presented for illustration.

For nominal or categorical data, frequencies and percentages (based on the non-missing sample size) will be tabulated for each category.

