#### 6.3 Hypothesis Testing

Unless otherwise specified all hypotheses will be tested at a 5% level of significance against two-sided alternative hypotheses.

Continuous variables will be analyzed by the following test procedures:

First of all the assumption of normally distributed data will be checked with Shapiro-Wilk test by treatment group. If the hypothesis of normally distributed data cannot be rejected for both treatment groups treatments will be compared by an ANCOVA procedure which includes "treatment" as the main factor and "baseline value" as covariate. T-Tests for independent samples will be used to compare groups at baseline.

In the event that the normality assumption is not warranted, data will be log-transformed and normality assumption of the transformed data will be checked by Shapiro-Wilk test. In case of non-rejection of the hypothesis of normally distributed data for both treatment groups, ANCOVA procedure and t-tests as described above will be performed on the basis of log-transformed data.

Point estimates and 95% CI of the difference in (adjusted) mean change from baseline will be provided if data are evaluated on basis of an ANCOVA procedure.

Otherwise Mann-Whitney's-U test on the basis of original data will be applied for comparison of groups at baseline. Mann-Whitney's-U test on the basis of intra-individual differences to baseline will be applied for treatment comparison per visits after baseline. Wilcoxon's signed rank test will be applied to evaluate changes from baseline per treatment group.

Categorical variables with 2 categories will be analyzed using Fisher's exact test (with Yates correction) to compare proportions between treatment groups. Variables with more than 2 categories will be compared by Pearson's Chi-square test. Additionally for each category, the proportions of treatment groups are compared using an (asymptotic) z test. Significant differences in proportions will be flagged, p-values for the z-test will not be shown.

Missing values will not be imputed.

If necessary, modifications of this general procedure will be described in the following sections of chapter 6.

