### 7.8.2 Safety Laboratory

Safety Laboratory			Original Data										
			Descriptive Statistics								Comparison of Groups		
Variable	Visit	Treatment	N	Missing	Mean	Median	STD	Min	Max	Effect	p-value	95% CI	
Hemoglobin	Day 0	Rivaroxaban											
		Aspirin											
	Week 2	Rivaroxaban											
		Aspirin											
	Week 8	Rivaroxaban											
		Aspirin											
	Week 20	Rivaroxaban								-			
		Aspirin											
	Week 28	Rivaroxaban											
		Aspirin											
	Week 36	Rivaroxaban								_			
		Aspirin											
	Week 52	Rivaroxaban											
		Aspirin											

				Comparison of					
Safety Laboratory CSV's			Total		Rivaroxaban		spirin	Proportions*	
		N	%	N	%	N	%	p-Value	
Total	Number of Patients								
Total	Number of Events								
Homoglobin	Number of Patients								
Hemoglobin	Number of Events								
	further variables								

\*can only be calculated for number of patients

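### The count of clinically significant laboratory values ignores the day-0 value, so abnormalities present before treatment can dilute the comparison between arms

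*SAP*

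**What the plan says.** SAP 6.12.2 plans two summaries of the safety laboratory. The first is "Descriptive statistics of original values and differences from baseline". The second is "The number (n) and percentage (%) of subjects with CSVs during study, depending on data". The second has no condition on the value before treatment and no rule on new onset or worsening.

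SAP 4.7.2 makes day 0 one of the sampling times: "Safety laboratory variables will be monitored (day 0, weeks 2, 8, 20, 28, 36, 52". The shell headed "Safety Laboratory CSV's" in SAP 7.8.2 has rows for patients and for events by arm, with a p-value comparing proportions of patients. It has no row or column for baseline status.

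The documents do separate old from new findings elsewhere. SAP 6.12.3 lists and summarises adverse events as treatment-emergent. Protocol 10.1.1 (Adverse event), whose term for a condition includes laboratory results, says that conditions present before consent and continuing "at unchanged intensity, are recorded as medical history".

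For continuous values, SAP 6.2 states: "Tables for original (untransformed) data will be provided as well as tables for differences from baseline by visit". SAP 6.3 compares the arms after baseline by ANCOVA with the baseline value as covariate or, if normality fails on both scales, by a Mann-Whitney test on changes from baseline. The 7.8.2 shell for haemoglobin has a single block of original data with columns for a group comparison, and no change-from-baseline block.

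**The concern.** The safety question for a laboratory value is whether treatment produced an abnormality. A patient who enters with a CSV and keeps it unchanged says nothing about that, yet the planned count makes that patient a case. Narrowing the window to visits after the first dose would not cure this, because a persisting CSV is seen at those visits too.

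Entry with an abnormal value is possible. For kidney function the limit in Protocol 4.11.2 is "chronic renal failure with eGFR < 15 ml/min (MDRD formula"), so eGFR or creatinine may be well outside normal at day 0. No numerical entry limit is given for haemoglobin, transaminases or bilirubin.

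If such patients are present in both arms, the ratio of the two proportions moves towards 1 and the test loses power. In a safety table the risk of attenuation is that a real signal is missed.

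The closing qualifier *depending on data* adds a second weakness. It may mean only that an empty table will not be printed, but as written it leaves the decision to produce the CSV summary until an open-label trial's data are known.

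**Working it through.** **Figures in the plan.** The documents give no figure for CSVs, so there is nothing to reproduce. The only input taken from them is 94 patients per arm (SAP 2.4). The test follows SAP 6.3: Fisher's exact test, two-sided 5%.

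**Assumptions.** Let b be the proportion of each arm with a CSV at day 0 that enters the count, either because day 0 itself is counted or because the CSV persists. Let p be the proportion with a new CSV among patients without one at day 0. The documents give neither, and CSV has no stated thresholds (the SAP abbreviations list only expands the term). The illustration uses b = 0% to 30% and p = 4% versus 14%.

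**Formulae.**
- Count as planned: rate per arm = b + (1 − b)p, with 94 per arm.
- New CSVs only: rate = p, with 94(1 − b) per arm.
- Difference between arms as planned = (1 − b)(0.14 − 0.04).

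Example at b = 10%: 0.10 + 0.90 × 0.04 = 13.6% and 0.10 + 0.90 × 0.14 = 22.6%. The ratio is 22.6/13.6 = 1.66 and the difference is 9.0 points instead of 10. For the new-onset count, 94 × 0.90 = 84.6, or 85 per arm.

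| b | Any CSV, by arm | Risk ratio | Power, any CSV | New CSVs: n per arm | Risk ratio | Power, new CSVs |
|---|---|---|---|---|---|---|
| 0% | 4.0% vs 14.0% | 3.5 | 60% | 94 | 3.5 | 60% |
| 10% | 13.6% vs 22.6% | 1.66 | 30% | 85 | 3.5 | 56% |
| 20% | 23.2% vs 31.2% | 1.34 | 19% | 75 | 3.5 | 48% |
| 30% | 32.8% vs 39.8% | 1.21 | 14% | 66 | 3.5 | 40% |

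Power is exact, summed over both binomial distributions.

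**Sensitivity to the assumed rates.** With new CSVs in 2% versus 10%, the risk ratio falls from 5.0 to 1.61, 1.30 or 1.18 at b = 10%, 20% or 30%. Power is 22%, 14% or 10%, against 48%, 40% or 33% for new CSVs only. The pattern is the same.

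**Shell against text.** SAP 6.12.2 and 6.2 require differences from baseline, and 6.3 requires comparison after baseline to take account of the baseline value. The vital-signs shell (7.8.1) has a change-from-baseline block carrying the arm comparison. The safety-laboratory shell (7.8.2) has none. The two instructions to the programmer do not agree.

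**The case against.** The strongest reply is that the SAP is silent on day 0. Listing it as a sampling time does not make it part of the CSV count. That is correct: a reader might infer that day-0 values are explicitly included, or that a persisting CSV is counted again at each visit in the events row, but no text says either. The point survives because a persisting CSV falls within the study period under any reading of the window.

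A reader might also infer from the shell that the arms are to be compared on raw values. The SAP text does not support this. Sections 6.12.2, 6.2 and 6.3 together call for changes and baseline-adjusted tests, and dashes in the shell leave it uncertain at which visits a comparison is meant. The shell is not unique either, since the compliance and exposure tables (7.4, 7.5) also compare arms on original data, though those variables have no day-0 value. What stands is a shell that omits a promised panel.

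Two further inferences fail. Raised UACR is one route to inclusion, but it is not a safety-laboratory variable, so it does not show that CSVs in this table are common at day 0. An eGFR above 15 that is abnormal need not be a CSV, and the protocol excludes some abnormality at entry, including low platelets and hepatic disease with coagulopathy.

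Finally, new abnormalities have another route. Laboratory findings can be adverse events, those that start or deteriorate after consent are recorded as such, and the major-bleeding definition already uses a fall in haemoglobin. This is a real but partial safeguard, because whether a laboratory finding is recorded as an adverse event rests on the investigator in an open-label trial. Transfusion and fatal bleeding are objective too, so the laboratory is not the only objective safety source.

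**Conclusion.** The point holds as a defect of specification. The CSV count and its between-arm test do not condition on the day-0 value, so pre-existing, unchanged CSVs attenuate the comparison. A count of new CSVs answers the safety question better and matches how the SAP treats adverse events.

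The size cannot be stated from the documents. With 94 per arm and assumed new-onset rates of 4% versus 14%, a day-0 prevalence of 10% to 30% cuts power to roughly half or a third of what the new-onset count offers (30% against 56%, down to 14% against 40%). With no CSVs at day 0 the two counts are identical. The effect is loss of contrast, not a systematic difference between arms, because randomisation balances pre-existing CSVs in expectation.

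The missing change-from-baseline panel is a separate and smaller inconsistency, to be settled in favour of the SAP text.

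**What to change.** In SAP 6.12.2 and table 7.8.2:

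1. Count a patient for a given variable only if a CSV first appears after the first dose and was not present at day 0. The denominator is patients without that CSV at day 0 who have at least one later value. Add a table of day-0 status by worst on-treatment status, so that worsening in patients already abnormal is still shown.
2. Add the change-from-baseline panel to the 7.8.2 shell, and make any arm comparison there by the SAP 6.3 procedure.
3. Delete *depending on data* from 6.12.2, so that the CSV summary is produced in any case.

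The cost is SAP wording and one reprogrammed table, with no new data. The downside is a somewhat smaller denominator for new CSVs (for example 85 instead of 94 per arm at 10% prevalence). The day-0 by worst-value table covers the patients who leave it.
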